### 8.2.7. Body Surface Area (BSA)

The percentage BSA affected will be summarised at each visit, including change and percentage change from baseline, by treatment group, using the FAS.

Change from baseline to Week 2 in the BSA will be analysed for the FAS with an ANCOVA model that includes baseline score, stratification variable (baseline EASI; ≤20 or >20) and treatment. The treatment effect will be estimated with the difference between the least square means (LS means), defined as ZPL521 - placebo. The estimate, standard error, 1-sided p-value, and 90% CI will be presented.

### 8.3. EXPLORATORY ENDPOINT

### 8.3.1. Ziarco Ointment Questionnaire

The categorical responses to the Ziarco ointment questionnaire will be summarised by treatment for each of the cohorts using the FAS. All data collected will be included.

All data will be listed.

#### 9. ANALYSIS OF PHARMACOKINETICS

#### 9.1. CONCENTRATION DATA

Cohorts 2 and 3 concentration data will be summarised for the PK analysis set at each visit and time point using descriptive statistics (n, median, minimum, maximum, missing and frequency of values <LOQ). The summary for Cohort 2 will be by treatment group and BSA treated and for

SAP Version v2.0 Page 31 of 43

Date: 16th March 2017

Cohort 3 by treatment group. For samples after the start of dosing only concentrations collected within a 15% window of the protocol specified time point will be included. Concentration values reviewed prior to the PK analysis and found to be unexpectedly high due to potential contamination will also be excluded. Values below the LLOQ will be taken as 0 for summaries.

An individual subject profile plot will be presented for the trough concentration data for Cohort 3 on the linear scale. The BSA treated will be presented along with the Subject ID. The actual sampling time will be used on the x-axis. Values below the LLOQ will be taken as 0 for linear plots.

All plasma concentration data will be listed for all cohorts. The listing will include BSA treated, actual sampling times and deviations from nominal sampling times. Values below the LLOQ will be listed as <LOQ (with relevant value for LOQ) in listings.

#### 9.2. PHARMACOKINETIC PARAMETER DATA

There is insufficient data to enable PK parameters to be calculated for Cohort 1 due to the very low and sporadic systemic exposure in a small number of subjects who had study ointment applied over 40% BSA.

The PK parameters for Cohort 2 will be summarised by BSA treated and Day for the PK analysis set. Geometric mean and CV will be presented for all parameters except  $t_{1/2}$ . Due to the low sporadic exposure  $T_{max}$  will not be summarized.

All PK parameters for Cohort 2 will be listed.

### 10. SAFETY

### 10.1. DRAIZE SCORE

The modified Draize score which assesses local toleration will be listed. This is only collected for Cohort 1.

#### 10.2. EXTENT OF EXPOSURE

For Cohorts 1 and 2, the number of days on treatment, the average daily volume administered and average daily amount of ointment used (based on a density of 1.1089 g/mL) will be summarised using descriptive statistics by treatment group for the FAS. The average daily volume administered and average daily amount of ointment used will be split by BSA treated within a cohort.

- Days on treatment = date of last dose date of first dose +1
- Daily volume administered = Total volume administered / number of days on treatment
- Daily amount of ointment used = daily volume administered \* density

SAP Version v2.0 Page 32 of 43

Date: 16th March 2017

For Cohort 3 the number of days on treatment and daily amount of ointment used will be summarised using descriptive statistics by treatment group for the FAS.

Daily amount of ointment used = (total weight of dispensed jars – total weight of returned jars) / days on treatment

If a jar is not returned then it will be assumed that the weight for this jar is missing and no daily amount of ointment used will be calculated for the subject.

Study drug administration, including all the variables specified above, will be listed.

#### 10.3. ADVERSE EVENTS

AEs will be coded using the latest MedDRA version available.

AEs will be considered treatment-emergent (TEAE) unless there is clear indication that the event occurred prior to first dose of study drug. AEs present prior to the first dose of study drug administration that increased in severity or relationship to study drug after the first dose of study drug will be classed as TEAE. Events with missing or partial dates will be handled such that in the absence of contradictory information an AE is treatment emergent. So for a missing start date (where stop date is after date of first dose or missing) the date will be imputed as the date of first dose; for a missing stop date the date will be imputed as the date of the subject's last study day. If a partial date is recorded, the following convention will be used to assign the AE:

- If a start date is missing the day information and month/year is the same as first dose date then use first dose date, else '01' will be used for the day; if a start date is missing the month and the year is the same as first dose date then use first dose date, else January will be used for the start month; if start date is missing (i.e. even the year is unknown) then the AE will be considered not treatment emergent and the date will be set to the date of informed consent.
- If a stop date is missing the day information and month/year is same as the subject's last study date then use last study date, else last day of the given month will be used for the stop day; if a stop date is missing the month and year is the same as last study date then use last study date, else December will be used for the stop month.

All AEs will be listed however only TEAEs will be included in the summary tables. An overall summary will present the number and percentage of subjects by treatment group and BSA treated for Cohorts 1 and 2 and by treatment group for Cohort 3. The summary will include:

- any TEAE
- any TEAE considered as related to study drug (evaluated by the investigator as Related, Possibly Related or Probably Related or not reported)
- any serious TEAE
- Maximum intensity TEAE of none, mild, moderate, severe; i.e. a subject with TEAEs at

SAP Version v2.0 Page 33 of 43

Date: 16th March 2017

different intensities will be summarised at the most severe intensity

- any TEAE leading to study drug discontinuation
- any TEAE leading to death

The table will also include the total number of TEAEs reported in each treatment group. The total number of unique terms within subjects will also be presented, counting each TEAE only once within each subject.

The number and percentage of subjects with TEAEs will be presented by SOC, PT and treatment group and BSA treated for Cohorts 1 and 2 and by SOC, PT and treatment group for Cohort 3. Subjects with multiple TEAEs within a SOC or SOC/PT combination will be counted only once for that SOC or SOC/PT combination. Similar summaries will be presented for related TEAEs.

Summaries of TEAEs by maximum intensity (Mild, Moderate, or Severe) will be presented for TEAEs.

All TEAEs will be listed by subject and start date. Separate listings of serious TEAEs and TEAEs leading to discontinuation of study drug will also be generated.

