### 15. INDEX OF LISTINGS

The following listings are planned to be generated and numbering is indicative only and may be updated for final reporting based on CSR requirements.

Listing	Title	Cohort
Number		
16.2.1.1	Subject Disposition by Cohort	1,2,3
16.2.1.2	Screen Failures by Cohort	1,2,3
16.2.2.1	Protocol Deviations by Cohort	1,2,3
16.2.3.1.1	Analysis Sets by Cohort	1,2
16.2.3.1.2	Cohort 3: Analysis Sets	3
16.2.4.1.1	Demography by Cohort	1,2
16.2.4.1.2	Cohort 3: Demography	3
16.2.4.2	Medical History by Cohort	1,2,3
16.2.4.3	Prior and Concomitant Medications by Cohort	1,2,3
16.2.5.1.1	Study Drug Administration by Cohort	1,2
16.2.5.1.2	Cohort 3: Study Drug Administration	3
16.2.5.2	Cohort 3: Study Drug Dispensed and Returned	3
16.2.6.1.1	EASI Total Score by Cohort	2,3
16.2.6.1.2.1	Cohort 3: EASI Components Derived	3
16.2.6.1.2.2	EASI Components by Cohort	2,3
16.2.6.1.3	Investigator Global Assessment (IGA) by Cohort	2,3
16.2.6.1.4	Cohort 3: Pruritus (Itch) Questionnaire	3
16.2.6.1.5	Cohort 3: Patient Global Impression of Change (PGIC)	3
16.2.6.2	Body Surface Area (BSA) by Cohort	2,3
16.2.6.3	Ziarco Ointment Questionnaire by Cohort	1,2,3
16.2.6.4.1	ZPL-5212372 Concentrations by Cohort	1,2,3
16.2.6.4.2	Cohort 2: Pharmacokinetic Parameters	2
16.2.7.1	Adverse Events by Cohort	1,2,3
16.2.7.2	Serious Adverse Events by Cohort	1,2,3
16.2.7.3	Adverse Events Leading to Discontinuation by Cohort	1,2,3
16.2.7.4	Cohort 1: Modified Draize Score	1
16.2.8.1.1	Haematology Clinical Laboratory Data by Cohort	1,2,3
16.2.8.1.2	Haematology Clinical Laboratory Data of Potential Clinical	1,2,3
	Concern by Cohort	
16.2.8.1.3	Chemistry Clinical Laboratory Data by Cohort	1,2,3
16.2.8.1.4	Chemistry Clinical Laboratory Data of Potential Clinical Concern	1,2,3
	by Cohort	
16.2.8.1.5	Urinalysis Clinical Laboratory Data by Cohort	1,2,3
16.2.8.1.6	Urinalysis Clinical Laboratory Data of Potential Clinical Concern	1,2,3
	by Cohort	
16.2.8.1.7	Serology and Screening Laboratory Data by Cohort	1,2,3
16.2.8.1.8	Pregnancy Test Data by Cohort	1,2,3

SAP Version v2.0 Page 42 of 43

Date: 16th March 2017

Listing Number	Title	Cohort
16.2.8.2.1	Vital Signs by Cohort	1,2,3
16.2.8.2.2	ECGs by Cohort	1,2,3
16.2.8.2.3	ECGs of Potential Clinical Concern by Cohort	1,2
16.2.8.2.4	Physical Examination by Cohort	1,2,3

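### SAP 10.3 gives two opposite classifications to an adverse event with no start date when the stop date is missing or after first dose

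*SAP*

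**What the plan says.** All of the relevant rules are in SAP section 10.3.

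- **Default.** An AE counts as treatment emergent "unless there is clear indication that the event occurred prior to first dose of study drug".
- **Principle for incomplete dates.** "Events with missing or partial dates will be handled such that in the absence of contradictory information an AE is treatment emergent".
- **Main sentence.** Applying that principle, it takes the first dosing day as the start: "for a missing start date (where stop date is after date of first dose or missing) the date will be imputed as the date".
- **End of the first bullet.** In the list that follows, introduced as the convention for partial dates: "if start date is missing (i.e. even the year is unknown) then the AE will be considered not treatment emergent". The start date is then set to the date of informed consent.
- **Worsening events.** Some earlier events become TEAEs in their own right: "AEs present prior to the first dose of study drug administration that increased in severity or relationship to study drug after the first dose".
- **Consequence.** "All AEs will be listed however only TEAEs will be included in the summary tables". Later in the section: "Separate listings of serious TEAEs and TEAEs leading to discontinuation of study drug will also be generated".

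**The concern.** The main sentence and the end of the first bullet both apply to an event with no start date at all, and they point in opposite directions. The main sentence looks at the stop date before deciding; the bullet does not. Two programmers could code the same event differently and each cite section 10.3.

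The bullet also runs against the section's own default. An unknown onset date is not a clear indication that the event began before dosing, yet the bullet treats it as one. It departs, too, from the direction taken for other missing AE information: protocol section 8.6 calls for conservative conventions, and SAP section 6.2.3 takes missing causality, seriousness and severity at their worst value. That section leaves dates to later sections, so it shows the direction only and does not settle the question.

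Safety and tolerability is the primary objective of Cohorts 1 and 2 and a secondary objective of Cohort 3 (SAP section 3.1). An event classed as not treatment emergent leaves all the AE summary tables and, as section 10.3 is worded, the serious and discontinuation listings. The choice should not be left until someone has seen the event.

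**Working it through.** **Step 1: apply both rules to every possible stop date.** Take an AE whose start date is wholly missing, with no recorded increase in severity or relationship after first dose.

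| Stop date | Main sentence | End of first bullet | Section default | Result |
|---|---|---|---|---|
| After first dose | First dose date, TEAE | Consent date, not TEAE | TEAE | Conflict |
| Missing | First dose date, TEAE | Consent date, not TEAE | TEAE | Conflict |
| On day of first dose | Not covered | Consent date, not TEAE | TEAE | Bullet against default |
| Before first dose | Not covered | Consent date, not TEAE | Not TEAE | Agree |

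The two specific rules collide in the first two rows. In the third only the bullet applies, and it contradicts the default. In the fourth the bullet is right.

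**Step 2: look for text that settles it.**

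- Protocol section 7.16.1.1 defines a TEAE by onset or worsening after at least one dose and has no rule for missing dates.
- SAP section 6.2.3 passes dates on to later sections.
- SAP section 7.4 (medications) has a counterpart to the main sentence, but none to the bullet's clause on wholly missing dates.
- SAP section 12 (changes from the protocol) does not mention the point.

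**Step 3: size, if one event is affected.** Planned group sizes come from SAP sections 3.2 and 3.3.

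- Cohorts 1 and 2, each: 3 sentinel subjects at 2:1 give 2 active and 1 placebo; the other 9 at 2:1 give 6 and 3. Overall: 2 + 6 = 8 active, 1 + 3 = 4 placebo.
- Cohort 3: 20 active, 10 placebo.

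The tables count subjects, so the 'any TEAE' row changes only if the event is that subject's sole TEAE. The change is then 1/n:

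| Column | Active | Placebo |
|---|---|---|
| Cohort 1 or 2, overall | 1/8 = 12.5 points | 1/4 = 25 points |
| Cohort 1 or 2, 40% BSA | 1/6 = 16.7 points | 1/3 = 33.3 points |
| Cohort 1 or 2, 10% BSA | 1/2 = 50 points | 1/1 = 100 points |
| Cohort 3 | 1/20 = 5 points | 1/10 = 10 points |

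If the subject has another TEAE, 'any TEAE' does not change; only the rows that depend on this event do. The BSA columns are included because SAP section 6.1 splits the AE tables for Cohorts 1 and 2 that way. These figures reflect small denominators and say nothing about how likely such an event is.

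**The case against.** The best defence is that the intended meaning is evident. The section states its principle twice, the main sentence applies it under a specific condition, and the bullet can be read as covering what is left: events that stopped before first dose, for which a consent date makes sense. That is probably what was meant, but the SAP does not say it, and the bullet's wording reaches further. Nor can the main sentence be confined to partial dates, because these are introduced separately after it.

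The second defence is rarity, and it stands. Onset date is a required item in AE reports (protocol section 7.16.1.3), Cohorts 1 and 2 stay in the unit until Day 9, baseline events are reviewed before dosing, AEs are asked about throughout treatment, and entries are monitored and queried. A start date with no year would mostly be a blank field that survived all of this.

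Third, the consequences are limited, and this also stands. The event remains in the listing of all AEs. The titles of listings 16.2.7.2 ("Serious Adverse Events by Cohort") and 16.2.7.3 are not restricted to TEAEs, so a serious or discontinuation event may still appear there. Cohort progression is decided at the safety review meetings (SAP section 11), not from these tables, and no formal test is planned on AE data.

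Finally, a stop date on the day of first dose lies outside the direct conflict between the two rules. That is correct. It is included in the fix because only the bullet covers it and the section's default points the other way.

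**Conclusion.** The concern holds. For an AE with no start date and a stop date that is missing or after first dose, SAP section 10.3 gives two incompatible classifications, and no other text resolves them. The bullet is wrong as written: it contradicts the section's own default and errs in the non-conservative direction.

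The likely effect is small and confined to final reporting. The documents give no count of AEs without a start date, and there may be none. The percentage-point changes assume planned group sizes, one affected subject and no other TEAE in that subject. This should be corrected, but it does not threaten the trial's conclusions.

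**What to change.** Make two edits in SAP section 10.3.

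1. Keep the last clause of the first bullet, but limit it to AEs whose start date is wholly unknown and whose stop date is before first dose. These stay non-treatment-emergent and are dated to informed consent.
2. Widen the stop-date condition in the main sentence to on or after first dose, or missing. State that an AE with a wholly unknown start date meeting that condition is dated to first dose and is treatment emergent. This also settles the day-of-first-dose case.

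The rule for events that increase in severity or relationship stays as it is.

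The cost is one clause limited and one sentence aligned, with no change to data collection. SAP section 2 allows amendments before database lock; after that it requires deviations to be documented in the clinical study report. The downside is a slightly higher TEAE count if an undated event in fact began before dosing, which is the direction the section already accepts.

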#### 10.4. LABORATORY EVALUATIONS

The change from baseline and percentage change from baseline in haematology, chemistry, and continuous urinalysis parameters will be summarised by treatment group using descriptive statistics. Discrete urinalysis parameters will be summarised with counts and percentages by treatment group. The number of normal and abnormal (low and high) records will also be summarised with counts and percentages by treatment group. Baseline and all protocol specified on treatment (i.e. on or before the date of last study medication plus 1) visit data will be summarised. If a baseline value is missing for a parameter, the screening value will be used as the baseline value.

Subjects who satisfy the criteria for values of potential clinical concern will be summarised and listed separately. The summary will present the number of subjects with at least one ontreatment visit value (including unscheduled visits) satisfying the criteria. The listing will include all data for the subject and parameter which satisfied the criteria. The record satisfying the criteria will be identified on the listing. The criteria are:

SAP Version v2.0 Page 34 of 43

Date: 16th March 2017

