### 6. GENERAL ASPECTS FOR STATISTICAL ANALYSIS

#### 6.1. GENERAL METHODS

All statistical tests for Cohort 3 will be 1-sided at the 0.05 level of significance and accompanied by a 2-sided 90% CI. There will not be any adjustments for multiple comparisons. No statistical testing will be performed with the data from Cohorts 1 and 2.

All summaries and listings will be presented by treatment group and by cohort. For Cohorts 1 and 2, adverse events and pharmacokinetic data will be presented by treatment group and BSA treated (10%, 40% and overall) to assess whether BSA impacts this data.

Only on-treatment records will be summarised for post-baseline visits, except follow-up, unless stated otherwise. A record is considered on-treatment if it is on or before the date of last study medication plus 1 day.

Continuous variables will be summarised using the number of observations (n), mean, standard deviation (SD), 95% Confidence interval (CI) of mean, median, minimum, and maximum. Geometric mean and coefficient of variation (CV) will be included for PK parameters, where appropriate. Categorical variables will be summarised using frequencies and percentages. The number of missing values will be presented in summary tables. The missing count will not include

SAP Version v2.0 Page 22 of 43

Date: 16th March 2017

subjects who have discontinued at earlier visits.

Unless otherwise specified, the estimated mean and median for a set of values should be printed out to 1 more decimal place than the original values, and standard deviations should be printed out to 2 more decimal places than the original values. The minimum and maximum should report the same number of decimal places as the original values. The coefficient of variation will always be reported as a percentage to 1 decimal place. Percentages will be displayed with 1 decimal place; except percentages will not be presented when the count is zero and 100% will be presented as an integer.

Unless stated otherwise, baseline will be defined as the last non-missing measurement prior to administration of the first dose of IMP.

In by-visit summary tables the baseline will be summarised using all available data, but also for each visit using only the baseline data from subjects with available data at the visit; hence the mean change from baseline will equal the mean visit value – mean baseline value.

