### 6.3. VISIT WINDOWS

There is no requirement for visit windows for Cohorts 1 and 2 as subjects will remain in the CRU for the duration of the study, so all assessments will be presented and analysed according to the visit assessment recorded.

For Cohort 3, all assessments will be presented and analysed according to the visit assessment recorded. Due to the short study duration visit windows will not be used. If possible, any early termination visits will be assigned to the closest study visit if they are on-treatment. Prior to database lock the data will be reviewed to identify any outlying visits and make decisions on how to deal with any issues. All decisions will be documented prior to database lock.

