**Table 2: Criteria for Laboratory Safety Values of Potential Clinical Concern** 

Category	Parameter	Criteria
Haematology	Haemoglobin	<0.8 x baseline
	Haematocrit	<0.8 x baseline
	WBC	<2.5 or >17.5 x 10  /mm 
	Platelets	$<75 \text{ or } >700 \text{ x } 10^3/\text{mm}^3$
Chemistry	GGT	>3 x ULN
	Creatinine	>1.3 x ULN
	Urea	>1.3 x ULN
	Glucose, fasting	<0.6 x LLN or >1.5 x ULN
	Uric acid	>1.2 x ULN
	Sodium	<0.95 x LLN or >1.05 x ULN
	Potassium	<0.9 x LLN or >1.1 x ULN
	Calcium	<0.9 x LLN or >1.1 x ULN
	Albumin	<0.8 x LLN or >1.2 x ULN
	Total protein	<0.8 x LLN or >1.2 x ULN
Urinalysis	Urine WBC	≥6/HPF
	Urine RBC	≥6/HPF

LLN=lower Limit of Normal; ULN=Upper Limit of Normal.

Liver function tests (ALT, AST, alkaline phosphatase and total bilirubin) will also be summarised. The number of subjects with any on treatment visit (including unscheduled visits) value either  $>1.5 \times ULN \text{ or } >2 \times ULN \text{ or } >3 \times ULN \text{ will be summarised for each liver function test parameter.}$ 

All laboratory data will be listed; change from baseline, percentage change from baseline and abnormal alerts will be included in the listings. Screening laboratory tests for serology, drug screen and breath alcohol test will be listed, but not summarised.

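### In Cohorts 1 and 2 the last-dose-plus-1 rule ends on Day 8, so the scheduled Day 9 safety labs fall outside all ten laboratory summary tables

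*SAP*

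**What the plan says.** SAP 6.1 sets a general filter: "Only on-treatment records will be summarised for post-baseline visits, except follow-up, unless stated otherwise". It then defines the term: "A record is considered on-treatment if it is on or before the date of last study medication plus 1 day".

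SAP 10.4 repeats the limit in three places:

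- Descriptive, categorical and normal/abnormal tables: "Baseline and all protocol specified on treatment (i.e. on or before the date of last study medication plus 1) visit data will be summarised".
- Clinical-concern tables: "The summary will present the number of subjects with at least one ontreatment visit value (including unscheduled visits) satisfying the criteria".
- Liver table: "The number of subjects with any on treatment visit (including unscheduled visits) value either" of three multiples of the upper limit of normal is exceeded.

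The listings are not limited in this way: "All laboratory data will be listed; change from baseline, percentage change from baseline and abnormal alerts will be included in the listings".

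The schedule comes from the protocol. Table 9 (footnote 13) and Table 10 (footnote 15) put the last application on the morning of Day 7. Sections 6.2.5 and 6.3.5 schedule haematology, chemistry and urinalysis on Day 9, 48 hours after that application. The only other in-house panel after baseline is on Day 4, before that morning's application (6.2.2, 6.3.2). Table 7 adds a panel at follow-up, 7 to 14 days after the last dose. Protocol 2.4 names laboratory safety tests among the primary safety endpoints of both cohorts.

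**The concern.** Day 9 is the only scheduled in-house panel taken after the full course, in the first topical use of this compound in humans (Protocol 1.4). The rule closes one day before it, and the SAP gives no reason. The wording fits Cohort 3, where the final dose is on the evening of Day 14 and the labs are on Day 15. Carried over unchanged to the in-patient cohorts, it drops their end-of-stay visit. Under 6.1 the result is odd: a value from 7 to 14 days after dosing may be summarised, while a 48-hour value may not.

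The liver tests are the most exposed. ALT, AST, alkaline phosphatase and total bilirubin are values of concern in Protocol Appendix 1, but they are not in SAP Table 2, and SAP Section 15 plans no clinical-concern listing for them. A raised Day 9 liver value would therefore show only in the full chemistry listing.

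At stake is the comparison by treatment group. With the rule as written, an active-versus-placebo view of the end-of-stay labs has to be rebuilt by hand from listings.

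**Working it through.** **1. The schedule.** Counting the visits with safety labs in Cohorts 1 and 2 gives screening, Day 1, Day 4, Day 9 and follow-up: 5 panels. Protocol Table 13 plans 5 haematology and 5 biochemistry samples, so the count agrees.

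**2. The cut-off.**

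| | Last dose | Last dose + 1 | End-of-treatment labs | Inside the rule? |
|---|---|---|---|---|
| Cohorts 1 and 2 | Day 7 (morning) | Day 8 | Day 9 = Day 7 + 2 | No |
| Cohort 3 | Day 14 (evening) | Day 15 | Day 15 | Yes |

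No safety labs are scheduled on Day 8 (Protocol 6.2.4, 6.3.4).

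**3. What the remaining in-house panel represents.** Applications over the course: 6 days × 2 + 1 = 13. Applications before the Day 4 sample: 3 days × 2 = 6. So 6/13 = 46% of the course had been applied.

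**4. Tables affected.** SAP Section 14 plans 3 haematology, 4 chemistry (including liver) and 3 urinalysis tables: 3 + 4 + 3 = 10, all covering Cohorts 1 and 2.

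- Four are clinical-concern or liver counts (14.3.4.1.3, 14.3.4.2.3, 14.3.4.2.4, 14.3.4.3.3), limited to on-treatment values.
- The other six (14.3.4.1.1, 14.3.4.1.2, 14.3.4.2.1, 14.3.4.2.2, 14.3.4.3.1, 14.3.4.3.2) are governed by the sentence that spells out the plus-1 limit.

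Day 9 is outside all ten.

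**5. Share of post-baseline panels omitted.** There are 3 per subject: Day 4, Day 9 and follow-up. SAP 6.1 exempts follow-up from the filter; SAP 10.4 names only baseline and on-treatment visits.

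- If 6.1 governs, Day 4 and follow-up are summarised and 1 of 3 panels is omitted.
- If 10.4 governs, only Day 4 is summarised and 2 of 3 are omitted.

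Day 9 is omitted in both cases.

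**6. Subjects.** At the planned 12 + 12 = 24 subjects and 2:1 allocation, the Day 9 panels come from 16 active and 8 placebo subjects. The 40% BSA groups have 9 subjects per cohort (6 active, 3 placebo), so 18 of the 24 panels (12 active, 6 placebo) are theirs.

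**7. Other Day 9 data.**

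- Vital signs, both cohorts: in-house time points after the first dose are 6 (Day 1) + 10 (Days 2 to 6) + 6 (Day 7) + 2 (Day 8) + 1 (Day 9) = 25. One of 25 (4%) falls outside the rule.
- ECG, Cohort 1: the same count, 1 of 25.
- PK, Cohort 2: a 48-hour sample is also drawn on Day 9. Read literally, 6.1 reaches it; SAP 9.1 plans summaries at each visit and time point, which may count as stating otherwise.

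**The case against.** The strongest objection is practical. Every Day 9 value is listed with abnormal alerts. The on-treatment limit is written for the clinical-concern summary and not for its listing, so a Day 9 value meeting the SAP Table 2 criteria may also appear there. Abnormalities reported as adverse events enter the AE tables, and SAP 10.3 sets no post-dose cut-off. Unscheduled samples up to Day 8 still enter the clinical-concern and liver counts, as do early-termination labs within 1 day of the last dose. Progression between cohorts rested on the Safety Review Team's own review of the data (Protocol 3.6), and the SAP already reports on those reviews. No testing is planned in these cohorts. All of this stands. It limits the consequence but does not supply the missing summary by treatment group.

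It could also be said that a sample 48 hours after the last dose is simply off treatment. That would be a defensible convention, but it sits poorly with 6.1, which lets the later follow-up panel in.

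A reader might infer three stronger points that the documents do not support:

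- **That SAP 6.3 contradicts 10.4 for the six descriptive tables.** SAP 6.3 says of Cohorts 1 and 2: "so all assessments will be presented and analysed according to the visit assessment recorded". That passage is about visit windows and settles which visit label a record carries, not which records are included. Its Cohort 3 paragraph uses the same wording alongside an on-treatment condition for early-termination visits. Inclusion is set by 6.1 and 10.4.
- **That half of the post-baseline panels are lost.** That holds only if follow-up is left out of the count; with follow-up, the share is 1 or 2 of 3.
- **That this is an undeclared departure from the protocol.** SAP Section 12 does not mention the filter. But Protocol 8.6 promises summaries by visit without setting a window, and Protocol 8 leaves detailed methods to the SAP. The point is too weak to press.

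**Conclusion.** The point holds and should be fixed. For subjects in Cohorts 1 and 2 who complete dosing, the stated rule ends on Day 8 and leaves the scheduled Day 9 labs out of all ten laboratory summary tables, including the clinical-concern and liver counts. The in-house summary then rests on a panel drawn after 46% of the applications. Separately, 6.1 and 10.4 do not agree on follow-up labs, so the omission is 1 or 2 of 3 post-baseline panels per subject.

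This is a gap in tabulation, not a loss of data, and nothing here suggests that cohort progression was affected. The conclusion assumes dosing to the morning of Day 7 and Day 9 labs on their scheduled day. The subject counts use planned enrolment, which Protocol Table 4 allows to be lower. The effect in other domains is small: 1 of 25 time points for vital signs and for the Cohort 1 ECG.

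**What to change.** For Cohorts 1 and 2 only:

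- State in SAP 6.1 and 10.4 that the scheduled Day 9 assessments are included in the laboratory summaries and in the clinical-concern and liver counts. Either name Day 9 as an exception, as 6.1 does for follow-up, or use last dose + 2 days as the window for safety data.
- State in 10.4 whether follow-up labs are summarised, in agreement with 6.1.
- Apply the same Day 9 rule to the 48-hour vital signs (10.5) and the Cohort 1 48-hour ECG (10.6).
- Confirm in 9.1 that the Cohort 2 48-hour concentration is summarised.

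The cost is SAP wording and one derivation flag, with no new data. The downside is that the tables would contain a sample taken 48 hours after the last dose and may show slightly more abnormalities. Cohort 3 efficacy summaries are unchanged.
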